# 5.2.3. Risk Assessment and Prophylaxis for Tumor Lysis Syndrome (TLS)

Venetoclax can cause rapid reduction in tumor and thus poses a risk for TLS in the initial rampup phase. Changes in blood chemistries consistent with TLS that require prompt management can occur as early as 6 to 8 hours following the first dose of venetoclax and at each dose increase.

Page | 18 04/25/2024

The risk of TLS is a continuum based on multiple factors, including tumor burden and comorbidities. Perform tumor burden assessments, including radiographic evaluation (e.g., CT scan), assess blood chemistry (potassium, uric acid, phosphorus, calcium, and creatinine) in all patients and correct pre-existing abnormalities prior to initiation of treatment with venetoclax. Reduced renal function (creatinine clearance [CrCl] <80 mL/min) further increases the risk.

Patients with ALL at high risk of tumor lysis should be assessed rapidly for evidence of symptomatic hyperleukocytosis, tumor lysis syndrome, and coagulopathy. Suggested initial studies, obtained prior to initiating antileukemia therapy, may include a complete blood count (CBC), prothrombin (PT) and activated partial thromboplastin times (aPTT)and serum electrolytes, including creatinine, BUN, uric acid, phosphorus, and calcium. Continued monitoring of these studies should be carried out at suitable intervals until abnormalities have resolved or the risk has abated.

Recommended TLS prophylaxis based on Tumor Burden from clinical trial data (consider all patient co-morbidities before final determination of prophylaxis and monitoring schedule) is shown in **Table 5**:

Table 5: TLS Prophylaxis

Tumor Burden		Prophylaxis		
		Hydration	Anti-hyperuricemics	
Low	Any LN <5cm AND ALC <25 x10°/L	Oral (1.5-2 L)	Allopurinol	
Medium	All LN >5cm to <10cm AND ALC $\geq$ 25 x10  /L	Oral (1.5-2 L) and consider additional intravenous	Allopurinol	
High	Any LN ≥10cm OR ALC ≥25 x10  /L AND any LN ≥5cm	Oral (1.5-2 L) and intravenous (150- 200 mL/hr as tolerated)	Allopurinol: consider rasburicase if baseline uric acid is elevated	

ALC = absolute lymphocyte count; LN = lymph node.

Administer intravenous hydration for any patient who cannot tolerate oral hydration.

Start allopurinol or xanthine oxidase inhibitor 2 to 3 days prior to initiation of venetoclax.

Evaluate blood chemistries (potassium, uric acid, phosphorus, calcium, and creatinine); review in real time.

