For patients at risk of TLS, monitor blood chemistries at 6 to 8 hours and 24 hours at each subsequent ramp-up dose.

**5.2.4. Drug Preparation, Storage and Handling.** Detail drug preparation instructions are provided in the manufacturer's full prescribing information brochure. Unused portions of the study drug will be discarded properly as per the institutional policies.

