#### 6.2. Recommended Venetoclax Dose Modification.

Interrupt dosing, reduce number of days, or reduce dose for toxicities. Treatment modifications for venetoclax related toxicities will be performed as per the respective summaries of product characteristics (SmPC). As CB-103 and venetoclax do not have overlapping toxicity, dose modification of CB-103 is independent of venetoclax dose modification: treatment modifications for CB-103 related are described in **Section 6.1.** 

See the following **Tables 14a and 14b** for dose modifications for hematologic and other toxicities related to **venetoclax**. For patients who have had a dosing interruption greater than 1 week reassess for risk of TLS to determine if reinitiation with a reduced dose is necessary.

Table 14a: Recommended Dose Modifications of Venetoclax for Toxicitiesa

Event	Occurence	Action
	•	Tumor Lysis Syndrome
Blood chemistry		Withhold the next day's dose. If resolved within 24 to 48 hours of last dose, resume at the same dose.
changes or symptoms	Any	For any blood chemistry changes requiring more than 48 hours to resolve, resume at a reduced dose.
suggestive of TLS		For any events of clinical TLS b , resume at a reduced dose following resolution.
		Non-Hematologic Toxicities
Grade 3 or 4 non-		Interrupt venetoclax. Once the toxicity has resolved to Grade 1 or baseline level, VENCLEXTA therapy may be resumed at the same dose. No dose modification is required. Consider decreasing treatment days.
hematologic toxicities	2nd and subsequent occurrences	Interrupt venetoclax. Follow dose reduction guidelines in Table 14b when resuming treatment with Venetoclax after resolution. Consider decreasing treatment days. A larger dose reduction may occur at the discretion of the physician.
		Hematologic Toxicities
Grade 3 or 4 neutropenia with infection or fever; or	1st occurrence	Interrupt venetoclax. To reduce the infection risks associated with neutropenia, granulocyte-colony stimulating factor (G-CSF) may be administered with Venetoclax if clinically indicated. Once the toxicity has resolved to Grade 1 or baseline level, Venetoclax therapy may be resumed at the same dose. Consider decreasing treatment days.

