# 8. STUDY CALENDAR (28 day Cycle) Table 16: Study Calendar

	Screening		Treatment Period							End of Treatment Visit 	Follow- Up 		
		Cycle 1					Cycle 2			From Cycle 3			
Day of cycle	-21 to -1	1 	5	26	28	1 	26	28	1 	26	28	1	
Assessments 													
Informed Consent	Х												
Demographics with body height (cm)	Х												
Medical History	Х												
Disease history (including number of prior therapy regimens for ALL)	Х												
Inclusion/Exclusion	X												
ID Panel	X 												
Pregnancy Test	X 	X 				X 			X 			X 	
Vital Signs and body measurements													
ECOG Performance Status	X	Χ				X			Χ			X	X
Weight (kg)	Х	Χ				X			Χ			X	X
Physical Exam	Х	Χ		X 		Χ	X 3		Χ	X 		X	X
Eye examination (see Section 8.4)	X			Х			X			Х		X	X
Body Temperature	Х	Х				X			Χ			X	X
Respiratory rate	Х	Х				X			Χ			X	Х
Cardiac assessments													
Blood Pressure	Х	Х		Х		X	Х		Χ	Х		X	
12-Lead EKG	X 	Х	Х			Χ			Χ			X	
ECHO or MUGA	X 	X 				X			Χ			X	
Standard Laboratory Procedures													
Biochemistry 	Х	Χ	Х	Х		X	Х		Χ	Х			
Hematology 	Х	Х	Χ	Х		X	Х		Χ	Х			
Coagulation 	Х	Х	Х	Х		X	Х		Χ	Х			
Disease Assessment 	Х	X 		Х		X 	Х		X 	Х			X 
Pharmacokinetic profile 		Х	Х										
Biomarker Assessments 		Х	Х	Х			Х			Х		Х	
Lumbar puncture & CSF sampling 	Х			Х			Χ			Х			
Concomitant Medications	Х	Х	Х	Х		Χ	Х		X 	X 			
Adverse Events	Х	Х	Х	Х		Χ	Χ		Χ	Х		Х	Х
Survival Status				_									Х

Protocol 2021-0547 4/25/2024

- 1. Assessments scheduled on days of dosing should be done prior to administration of study drug(s), unless otherwise specified.
- 2. Screening assessments can be used as day 1 assessments of cycle 1 if done within the previous 72 hrs.
- 3. End of previous cycle assessments (Day 26) can be used as day 1 assessments if done within Day 26-29. If subsequent cycle is delayed, hematology, chemistry, and coagulation labs and physical exam assessments should be repeated on Day 1 of cycle.

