- 4. For women of childbearing potential only. Serum pregnancy test must be performed within 24-48 hours before first study treatment. During the on-treatment period and at the EoT visit, urine pregnancy testing should be done as indicated in the table or whenever a pregnancy is suspected. Pregnancy and suspected pregnancy occurring while the patient is on study drug treatment or within 90 days after the last dose of CB-103 should be reported to the supporting company (Cellestia AG).
- 5. Screening assessments can be used as day 1 assessments if done within the previous 14 days.
- 6. EKG and LVEF assessment by ECHO or MUGA should be done within 14 days before first study treatment: these assessments may be repeated at the Investigator's discretion in case of signs or symptoms of cardiotoxicity. See Sections 8.7.1 and 8.7.2.
- 7. Tests will be performed at least 2 times weekly during the first treatment cycle and at least 1 time weekly during each successive treatment cycle. Outside labs will be permitted and the PI/treating physician will review the labs for clinical significance, and sign/date the results. If patients present treatment-related toxicities, monitor blood counts and chemistries as clinically indicated. This assessment does not need to be repeated at Cycle 1, Day 1 if it was performed at screening within 48 hours prior to start of study treatment.
- 8. Laboratory tests to be performed locally, within 48 hours before study visit (Day 1 of each cycle, including Cycle 1, Day 1) include albumin, alkaline phosphatase, alanine aminotransferase (ALT), aspartate aminotransferase (AST), lactate dehydrogenase (LDH), carbon dioxide (CO2), uric acid, calcium, chloride, glucose, phosphorus, potassium, sodium, magnesium, total bilirubin, direct bilirubin (if total bilirubin is elevated above the upper limit normal), total protein, blood urea nitrogen (BUN) and creatinine.
- 9. CBC (WBC with differential, unless WBC <0.5 x109/L in which case differential not needed, Hemoglobin, and Platelet count).
- 10. Prothrombin time (PTT), activated partial thromboplastin time (aPTT), and fibrinogen. This assessment does not need to be repeated at Day 1 of cycles if it was performed within 3 days prior.
- 11. Disease assessment:
  - Bone marrow samples (aspirate and/or biopsy), cytogenetics, and flow cytometry: screening assessment can be used as day

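### The hour-timed TLS chemistry rule in section 5.2.3 leaves out the first venetoclax dose, which the same section names as a risk time

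*Combined protocol and SAP*

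**What the plan says.** Section 5.2.3 gives two times at which TLS-type chemistry changes may appear. It says they "can occur as early as 6 to 8 hours following the first dose of venetoclax and at each dose increase". One rule in that section attaches hours to a venetoclax dose: "For patients at risk of TLS, monitor blood chemistries at 6 to 8 hours and 24 hours at each subsequent ramp-up dose".

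Three other instructions in 5.2.3 reach the first dose without naming an hour:
- a general one: "Evaluate blood chemistries (potassium, uric acid, phosphorus, calcium, and creatinine); review in real time";
- one in the paragraph on ALL patients at high risk of tumor lysis: "Continued monitoring of these studies should be carried out at suitable intervals until abnormalities have resolved or the risk has abated";
- one in the lead-in to Table 5, which asks the site to "consider all patient co-morbidities before final determination of prophylaxis and monitoring schedule".

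The study calendar (Table 16) places Cycle 1 biochemistry on Days 1, 5 and 26. Footnote 1 says: "Assessments scheduled on days of dosing should be done prior to administration of study drug(s), unless otherwise specified". Footnote 7 says: "Tests will be performed at least 2 times weekly during the first treatment cycle". Section 8 asks that patients be admitted for Cycle 1 Days 1–7.

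The action rule is in Table 14a (section 6.2). For chemistry changes or symptoms suggestive of TLS, it says: "Withhold the next day's dose. If resolved within 24 to 48 hours of last dose, resume at the same dose".

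**The concern.** The section identifies the hours after the first dose as a danger period and then writes a timed monitoring rule that starts with the second dose. The next dose is double the first and comes about a day later. Table 14a makes that dose conditional on chemistry or symptoms, yet no value at a set post-dose hour is required to inform the decision.

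What is at stake is the safety of the step from Day 1 to Day 2. Eligibility admits some patients whom the protocol itself regards as higher risk. Criterion 3.1.7.2 accepts a creatinine clearance of 50 mL/min or more when serum creatinine exceeds 1.5 times the upper limit of normal, while 5.2.3 says a clearance below 80 mL/min raises the TLS risk. Sections 3.1 and 3.2 set no ceiling on the white cell count.

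**Working it through.** The plan states no figure to reproduce here. The check sets the dose times against every chemistry requirement and then counts.

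**Inputs**
- Standard ramp (Table 2): 100 mg on Day 1, 200 mg on Day 2, 400 mg from Day 3.
- Strong CYP3A inhibitor ramp (Table 3): 10, 20, 50 and 100 mg on Days 1–4 (70 mg on Day 4 with posaconazole).
- Earliest onset (5.2.3): 6–8 h after the first dose and at each increase.
- Timed draws (5.2.3): 6–8 h and 24 h, at each subsequent ramp-up dose, in patients at risk of TLS.
- Assumption: daily doses are about 24 h apart.

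**Timeline on the Table 2 ramp**

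| Time from first dose | Event | Chemistry required at a set post-dose hour |
|---|---|---|
| 0 h | 100 mg | none (the calendar draw is pre-dose) |
| 6–8 h | earliest onset named in 5.2.3 | none |
| about 24 h | 200 mg | none |
| about 30–32 h | 6–8 h after the Day 2 dose | first timed draw |
| about 48 h | 400 mg | 24-h draw for the Day 2 dose |

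**Calculations**
- First timed value: 24 + 6 = 30 h to 24 + 8 = 32 h after the first dose.
- Lag behind the earliest stated onset: 30 − 6 = 24 h; 32 − 8 = 24 h.
- Dose given by then: 100 + 200 = 300 mg (Table 2); 10 + 20 = 30 mg (Table 3).
- Draws covered, Table 2: 3 steps × 2 = 6 if every step counted; 2 subsequent steps × 2 = 4. So 4 of 6.
- Draws covered, Table 3: 4 steps × 2 = 8; 3 subsequent steps × 2 = 6. So 6 of 8.
- Lead time if a 6–8 h draw followed the first dose: 24 − 8 = 16 h to 24 − 6 = 18 h before the Day 2 dose.

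**Does anything else supply the missing value?**
- Section 8.9 and Table 16 footnote 8 ask for chemistry within 48 h before Day 1. That precedes the first dose and cannot show its effect.
- The twice-weekly minimum in footnote 7 is not tied to venetoclax doses. The pre-dose Day 1 draw plus Day 5 would meet it in week 1.
- The real-time review, the suitable intervals and the individualised schedule give no hour. Neither does the Days 1–7 admission.
- Table 14a says what to do with an abnormal value but not when to obtain one.
- The protocol does set clock times on Cycle 1 Day 1 for other purposes: sections 8.7.1 and 8.8 time the ECGs and the CB-103 pharmacokinetic samples by hour. TLS chemistry has no such entry.

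The count of required values at a set hour between the first dose and the Day 2 step is therefore 0. Extending the rule to the first dose would make it 2.

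**The case against.** The strongest counter-argument is that the sentence is awkward and can be read differently. It has two phrases beginning with *at* and no connector, and *subsequent* presupposes a dose already in view. Read beside the earlier warning, it might mean 6–8 h and 24 h after the first dose, and again at each later step. On that reading there is no gap, and every figure above falls away. The lines after Table 5 also look like unanchored table notes, so a phrase may have been lost; the documents do not settle that. This reading is strained, and a safety instruction open to both readings needs the same rewording.

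The second argument is that the first dose is already well protected. Baseline chemistry is assessed and corrected in all patients, allopurinol or another xanthine oxidase inhibitor starts 2–3 days before, patients should be in hospital, and Table 14a acts on symptoms as well as chemistry. All of this stands. It bounds the risk and makes early draws likely, but it does not require one at any stated hour.

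Third, section 5.4 links the venetoclax prescribing information and section 6.2 defers to the SmPC. Whether either sets draw times after the first dose cannot be judged from these documents. Section 5.4 offers the link as product information and does not itself require a draw.

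Fourth, requiring the 24-hour result before each step goes beyond adding the first dose. That is a fair point about scope. The review makes explicit what the real-time review and the Table 14a hold already need, but it may delay a dose.

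**Conclusion.** The concern holds. As written, 5.2.3 names the first venetoclax dose as a TLS risk time and omits it from its only hour-timed post-dose rule. The first required value at a set post-dose hour comes about 30–32 h after the first dose, 24 h later than the earliest onset the protocol gives and after two doses. From the Day 2 dose onward, the timed draws do support Table 14a.

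The conclusion rests on the literal reading of the sentence, on doses about 24 h apart, and on counting only values timed from a venetoclax dose. It applies to patients at risk of TLS and to the first dose only. It is a gap in a safety instruction that should be closed, with the residual risk limited by the prophylaxis, baseline correction and inpatient stay already planned.

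**What to change.** Reword the timed rule in 5.2.3 so that, in patients at risk of TLS, chemistries are drawn at 6–8 h and 24 h after the first dose as well as after every later ramp-up dose, and the 24-hour value is reviewed before the next step is given. Add a footnote to the biochemistry row of Table 16 that points to 5.2.3 for the ramp-up draws.

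The cost is a short change to one sentence and one footnote, plus two local chemistry draws per at-risk patient within the planned Days 1–7 stay. The documents do not say how many patients will be at risk. Over up to 30 patients the total is 2 × (0 to 30) = 0 to 60 draws. Waiting for the 24-hour result may push the next dose back by the laboratory turnaround time, which the documents do not give.

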# 5.3. Intrathecal Dosage and Administration.

Patients will receive intrathecal chemotherapy as per standard of care. Methotrexate, Cytarabine, hydrocortisone, or a combination of these is allowed on the study. The number of lumbar punctures with Intrathecal chemotherapies will depend on the age of the patient, clinical status, comorbidities, etc and will be determined by the PI.

**5.4.** Venetoclax is commercially available. Commercial supply of each will be used. Detail product information may be found in the product prescribing information and available through the following links:

# **5. 4.1.** Venetoclax:

https://www.accessdata.fda.gov/drugsatfda\_docs/label/2016/208573s000lbl.pdf

**5.5.** Patients with PR or stable disease (SD) after the reinduction cycle may continue the treatment with the combination of CB-103 and venetoclax for a maximum of three additional cycles or until disease progression or bone marrow transplantation, whicher comes first.

#### 6. DOSE MODIFICATIONS

# 6.1. Recommended CB-103 Dose Modification.

The follow-up evaluations for toxicities apply during or beyond cycle 1 of the study.

The following sections outline the specific dose modifications for CB-103 for non-haematologic toxicities and should be followed by the Investigator accordingly. One dose level reduction indicated in case of moderate/severe non-haematological toxicities in the following **Tables** corresponds to a 100mg reduction per dose of CB-103, e.g. from 500mg BID to 400 mg BID intermittent schedule.

As CB-103 and venetoclax do not have overlapping toxicity, dose modification of venetoclax is independent of CB-103 dose modification: treatment modifications for venetoclax related toxicities will be performed as per Venetoclax Summaries of product characteristics (SmPC).

# 6.1.1. Dose modification for renal toxicity (Table 7).

If serum creatinine  $\geq 2$  x ULN has been demonstrated, this parameter must be repeated at least twice a week until resolution to  $\leq$  CTCAE grade 1, to allow for initiation of re-treatment and then at least weekly until either resolution or until stabilisation.

If proteinuria or haematuria  $\geq$  CTCAE grade 2 or serum creatinine  $\geq$  2.0 x ULN has been demonstrated, a 24-hour urine collection must be obtained for total protein and total creatinine and must be repeated at least weekly until either resolution to baseline value to allow for initiation of re-treatment, or until stabilisation. Whenever a measured CrCl is obtained, a serum creatinine value should be obtained within  $\leq$  72 hours of the urine collection.

Table 7: Dose modifications for renal toxicities

Dose Modifications for CB-103		
Worst Toxicity  CTCAE Grade unless otherwise specified (Value)  At any time during a cycle of CB-103 (including intended day of dosing)		
Serum creatinine		
(< 2 x ULN)	Maintain dose level	
(2 - 3 x ULN)	Omit dose administration until resolved to ≤ Grade 1, • If resolved in ≤ 7 days, then maintain dose level • If resolved in > 7 days, then ↓ 1 dose level	
Grade 3 (> 3.0 - 6.0 x ULN) & Grade 4 (> 6.0 x ULN)	Omit dose administration and discontinue patient from study treatment	

Abbreviations: AE, adverse event; CTCAE, Common Terminology Criteria for Adverse Events; LLN, lower limit of normal; ULN, upper limit of normal. Grading according to NCI-CTCAE v.5.0 guideline.

# 6.1.2. Dose modification for liver toxicity (Table 8).

If bilirubin or AST/ALT > CTCAE grade 2 has been demonstrated, these parameters must be repeated at least twice a week until resolution to < CTCAE grade 1, to allow for initiation of re-treatment and then at least weekly until either resolution or until stabilisation.

Page | 20 04/25/2024

Patients with total bilirubin > ULN (any duration) should have fractionation of bilirubin into total/direct or indirect/direct components and any additional work-up as clinically indicated by these results. Follow-up of hyperbilirubinaemia should proceed as per the guidelines above, irrespective of the results of fractionation.

**Table 8:** Dose modifications for hepatic toxicities

Dose Modifications for CB-103			
Worst Toxicity CTCAE Grade unless otherwise specified (Value)	At any time during a cycle of CB-103 (including intended day of dosing)		
Bilirubin			
Grade 1 (< 1.5 x ULN)	Maintain dose level		
Grade 2 (1.5 - 3 x ULN)	Omit dose administration until resolved to ≤ Grade 1,  • If resolved in ≤ 7 days, then maintain dose level  • If resolved in > 7 days, then ↓ 1 dose level		
Grade 3 (> 3–0 - 10.0 x ULN)	Omit dose administration until resolved to $\leqslant$ Grade 1, then $\downarrow$ 1 dose level		
Grade 4 (> 10.0 x ULN)	Omit dose administration and discontinue patient from study treatment		
AST or ALT			
Grade 1 (> ULN - 3.0 x ULN) & Grade 2 (>3.0 - 5.0 x ULN) without increase in total bilirubin >2 x ULN	Maintain dose level		
Grade 3 (> 5.0 - 20.0 x ULN) without increase in total	Omit dose administration until resolved to ≤ Grade 1 (or ≤ Grade 2 in case of liver metastasis), then		
bilirubin >2 x ULN	• If resolved in $\leqslant$ 7 days, then maintain dose level		
	• If resolved in > 7 days, then ↓ 1 dose level		
Grade 4 (> 20.0 x ULN) without increase in total bilirubin >2 x ULN	Omit dose administration until resolved to ≤ Grade 1, then ↓ 1 dose level		

Abbreviations: AE, adverse event; ALT, alanine aminotransferase; ANC, absolute neutrophil count; AST, aspartate aminotransferase; CTCAE, Common Terminology Criteria for Adverse Events; LLN, lower limit of normal; PLT, platelets; ULN, upper limit of normal. Grading according to NCI-CTCAE v.5.0 guideline.

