# **5.1.3.** Dosage and Administration.

CB-103 will be administered orally as 500 mg twice a day (BID) for 5 days on and 2 days off, which has now been declared the RP2D in adults (section 2.3.2 Clinical Studies), until disease progression per investigator's judgement, or until unmanageable drug related toxicity, or as long as the patients are continuing to derive clinical benefits (section 4.2 Treatment Plan). For patients already enrolled prior to Protocol Version 2.0, they will be reconsented and offered the increased dose if it is felt to be safe and in the patient's best interest by the treating physician, otherwise they may continue at their current dose of 500 mg daily.

Page | 15 04/25/2024

In the event of vomiting, no re-dosing will be provided. According to FDA recommendations, as for  $\geq$  12-year-old adolescent patients no weight-related clinically relevant effect on drug pharmacokinetics or safety are expected,  $\geq$  12-year-old adolescent patients enrolled in this trial may receive the same fixed daily dose as administered in adults (Clinical Growth Charts web page under National Center for Health Statistics at the Centers for Disease Control and Prevention website (https://www.cdc.gov/growthcharts/clinical\_charts.htm).

CB-103 will be provided as capsules of 100 mg each. Patients will be instructed to swallow the CB-103 capsules whole with a glass of water (approx. 200 mL) in the morning, on an empty stomach, at least one hour before taking breakfast; in the evening, within 8 to 12 hours of the first intake, at least one hour before the evening meal. Capsules should not be chewed prior to swallowing. Capsules that are broken, cracked, or otherwise damaged should not be ingested. In the exceptional case of a patient who is unable to swallow capsules, the capsules can be opened and the contents may be mixed in a spoon with a bit of yogurt or fruit puree in order to swallow and follow with a glass of approximately 200mL of water (IMP Manual).

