- **8.9.3. Biochemistry**: Clinical Chemistry includes albumin, alkaline phosphatase, alanine aminotransferase (ALT), aspartate aminotransferase (AST), lactate dehydrogenase (LDH), carbon dioxide (CO2), uric acid, calcium, chloride, glucose, phosphorus, potassium, sodium, magnesium, total bilirubin, direct bilirubin (if total bilirubin is elevated above the upper limit normal), total protein, blood urea nitrogen (BUN) and creatinine. Clinical Chemistry will be performed at least 2 times weekly during the first treatment cycle and at least 1 time weekly during each successive treatment cycle.
- **8.9.4. Pharmacodynamic/Biomarker Assessments**: Serial blood, CSF, and bone marrow samples will be obtained if additional fluid is available to measure gene and protein expression levels of relevant pathways (e.g. NOTCH, BCL2) as well as for longitudinal monitoring of tumor evolution by NGS. Results will not be limiting for patient enrollment. The samples will be analyzed by Cellestia and/or their designated laboratory (ies) from the list below:
- Cellestia R&D (Switzerland)
- SGS (Switzerland)

Blood and bone marrow samples are mandatory at baseline for local evaluation. For all patients, repeated blood sampling and bone marrow biopsy will also be taken at completion of induction, reinduction cycles ± 3 days, and at time of progression. An additional blood sample to monitor target engagement (PD) will also be collected on C1D5 at one of the PK sampling timepoints and Day 26 of all cycles of treatment. Except for the baseline, blood samples must be taken on the last week-day of CB-103 intake before the 2 days off treatment.

Details on sample collection requirements, preparation, processing, storage, and shipment will be provided in a separate laboratorymanual.

Page | 33 04/25/2024

Changes to the sampling scheme may be implemented based on the emerging data. Any adjustment will be recorded in the study file and the total number of samples taken will not be exceeded.

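### Table 8 has no AST/ALT row for total bilirubin above 2 x ULN, so in one narrow case CB-103 may restart at full dose after Grade 4 AST/ALT that would require a reduction on its own

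*Combined protocol and SAP*

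**What the plan says.** Section 6.1 says that the dose-modification sections "should be followed by the Investigator accordingly". It defines one level as 100 mg per dose, "e.g. from 500mg BID to 400 mg BID intermittent schedule". The study dose in section 5.1.3 is "500 mg twice a day (BID) for 5 days on and 2 days off".

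Table 8 in section 6.1.2 has two blocks.

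- **Bilirubin.** The row "Grade 2 (1.5 - 3 x ULN") says to hold, then resume at the same dose if resolved to Grade 1 or better in ≤7 days, or one level lower if it takes longer. Above 3 and up to 10 x ULN: hold, then reduce one level. Above 10 x ULN: discontinue.
- **AST or ALT.** Grades 1 and 2: no change. The next row, "Grade 3 (> 5.0 - 20.0 x ULN) without increase in total" bilirubin >2 x ULN, says to hold, then same dose if resolved in ≤7 days, otherwise one level lower. The last row, "Grade 4 (> 20.0 x ULN) without increase in total bilirubin >2 x ULN", says to hold, then reduce one level whatever the time to resolution.

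The Grade 1–2 AST/ALT row carries the same bilirubin qualifier. The text above the table requires repeat testing of bilirubin and AST/ALT "until resolution to < CTCAE grade 1, to allow for initiation of re-treatment".

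**The concern.** The bilirubin qualifier on the AST/ALT rows has no counterpart row. Once total bilirubin exceeds 2 x ULN, no AST/ALT row applies as printed, and the bilirubin row alone decides the restart dose. For bilirubin of >2 to 3 x ULN that row can be milder than the AST/ALT row it displaces. The worse liver injury would then allow a higher restart dose than the lesser one.

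What is at stake is the restart dose after a hold, in a drug for which section 2.3.2 lists two related serious events of drug-induced liver injury (N=79, both in patients with progressive liver metastasis). No estimate or test is involved.

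**Working it through.** The plan gives no figure to reproduce. The check reads Table 8 literally and compares two actions: the one required for a given AST/ALT grade alone, and the one set by the bilirubin row when bilirubin is >2 x ULN.

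**Step 1: code the actions.** 0 = no change; 1 = hold, then same dose; 2 = hold, then one level down; 3 = discontinue.

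| Row | Resolved ≤7 days | Resolved >7 days |
|---|---|---|
| AST/ALT Grade 1–2 alone | 0 | 0 |
| AST/ALT Grade 3 alone | 1 | 2 |
| AST/ALT Grade 4 alone | 2 | 2 |
| Bilirubin >2–3 x ULN | 1 | 2 |
| Bilirubin >3–10 x ULN | 2 | 2 |
| Bilirubin >10 x ULN | 3 | 3 |

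**Step 2: one shared 7-day clock.** 3 AST/ALT rows x 3 bilirubin bands x 2 times = 18 cells. The bilirubin action is stricter in 11, equal in 6 and milder in 1. The milder cell is Grade 4 AST/ALT with bilirubin >2–3 x ULN, all resolved in ≤7 days: action 1 against action 2.

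**Step 3: a separate clock for each parameter.** 3 x 3 x 2 x 2 = 36 cells: 23 stricter, 10 equal, 3 milder. All three milder cells have bilirubin >2–3 x ULN resolving in ≤7 days:

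- Grade 4 AST/ALT, ≤7 days (the cell from step 2);
- Grade 4 AST/ALT, >7 days;
- Grade 3 AST/ALT, >7 days.

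**Step 4: limits on those cells.** AST/ALT passes through lower grades as it recovers. In the two slow cells, a reading >5 x ULN taken once bilirubin is ≤2 x ULN meets the printed Grade 3 row, which requires a reduction because resolution takes >7 days. These two cells therefore survive only if AST/ALT is already ≤5 x ULN when bilirubin reaches ≤2 x ULN. The fast Grade 4 cell is not removed this way, since the Grade 3 row gives the same dose for ≤7 days. It does require that no reading >20 x ULN is taken while bilirubin is ≤2 x ULN. So 3 of 36 is an upper count. The denominator is also a matter of layout: splitting AST/ALT Grades 1 and 2 makes it 3 of 48.

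**Step 5: how fast recovery must be in the shared-clock cell.** The number of halvings is log2(start/target), and the longest half-life is 7 days divided by that number.

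- Target ≤3 x ULN (Grade 1 or better, as in the table): log2(20/3) = 2.74 halvings; 7/2.74 = 2.56 days (unrounded divisor).
- Target ≤ULN (if the strict inequality in the text above the table is literal): log2(20) = 4.32 halvings; 7/4.32 = 1.62 days.

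**Step 6: size of the dose difference.** There are 20 dosing days in a 28-day cycle at 5 on, 2 off. Same dose: 2 x 500 x 20 = 20,000 mg. Reduced: 2 x 400 x 20 = 16,000 mg. Ratio: 1000/800 = 1.25.

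**Step 7: look for a rule elsewhere.** Section 4.3 permits reductions at the physician's discretion but requires none. Sections 4.3.3 and 11 leave discontinuation for toxicity to judgement. Table 13 covers non-laboratory toxicities. The text above Table 8 governs recovery, not dose.

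**The case against.** The best case for the plan is that the gap has almost no practical content. CB-103 is held in every combined case. The text above Table 8 names both parameters together, which favours a shared clock and leaves a single cell that needs very fast recovery. The restart dose is the ordinary study dose; section 2.3.2 reports that no MTD was reached and that exposure was saturated there, so 25% more drug need not mean 25% more exposure. A sensible physician could reduce under section 4.3. All of this stands, and it is why the point is minor.

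Two further arguments do not close the gap. Combined injury could be recorded as a liver-injury diagnosis and handled under Table 13, but that table is for non-laboratory events and nothing directs laboratory-defined liver injury there. Table 8 heads its first column as worst toxicity, but that does not restore an AST/ALT row whose own condition excludes the patient. The sponsor chose a mandatory reduction after Grade 4 AST/ALT alone, and nothing in the protocol explains dropping it when bilirubin rises as well.

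A reader might infer that combined liver injury has no rule, or is generally treated more leniently. Table 8 does not support this: bilirubin >2 x ULN always forces a hold, >3 x ULN a reduction and >10 x ULN discontinuation. A reader might also infer that the toxicity monitoring in section 12 is compromised. It is not: a possibly or probably related grade ≥3 AST/ALT event in the first 28 days counts whichever row sets the restart dose.

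**Conclusion.** The inversion is real on the printed text and minor. It is firm in one case: AST/ALT >20 x ULN with bilirubin peaking at >2 to 3 x ULN, both resolved in ≤7 days. There the table permits 500 mg BID, where the same AST/ALT alone requires 400 mg BID. This holds on either reading of the 7-day limit. Separate clocks add at most two more cells, both conditional on the sampling pattern in step 4.

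The cell counts say nothing about how often this will happen. The documents give no rate for combined elevation, and the speed of recovery required suggests it will be rare among at most 30 patients. Efficacy conclusions and the stopping rule are unaffected.

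The conclusion assumes that Table 8 ends with the Grade 4 AST/ALT row, as the public text shows. The sponsor should confirm that against its own copy.

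**What to change.** Add one row to Table 8 for AST/ALT elevation with total bilirubin >2 x ULN. Its action should be the stricter of the bilirubin row and the AST/ALT row for that grade read without the qualifier. For AST/ALT >20 x ULN this means hold, then reduce at least one level regardless of time to resolution; the sponsor may prefer discontinuation. Add a sentence that the strictest applicable action governs. The recovery text above the table can stay as it is.

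Taking the maximum of the two action codes removes every milder cell (1 to 0 on a shared clock, 3 to 0 on separate clocks) and changes no other cell, so the clock question need not be settled first.

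The cost is one row and one sentence, plus a few more CB-103 reductions. No tests are added: under section 8.9.3 "Clinical Chemistry will be performed at least 2 times weekly during the first treatment cycle" and at least weekly after that, and the panel already includes AST, ALT and total bilirubin.
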